Testing "Ultraprocessed" Front-of-package Label Among Brazilian Consumers

Hypotheses and Analytic Plan

NCT #05842460

May 11th 2023

Hypotheses

The goal of this study is to examine whether combined “ultraprocessed” and nutrient warning labels are more effective than nutrient warning labels alone at reducing purchase intentions of food and beverage products. Therefore, our primary hypothesis is that participants who see the combined “ultraprocessed” and nutrient warning labels will report a lower likelihood of purchasing the product than participants who see only nutrient warning labels (H1).

We will also examine the effect of combined “ultraprocessed” and nutrient warning labels on precursors to behavior change. Thus, we also hypothesize that, compared to nutrient warning labels alone, exposure to combined “ultraprocessed” and nutrient warning labels will lead to:

- Lower perceived product healthfulness (H2)
- Higher likelihood of identifying all products presented as ultraprocessed (H3)
- Higher perceived message effectiveness (H4)

Main Analyses

We will use a two-sided critical alpha of 0.05 to conduct all statistical tests. All confidence intervals presented will use a 95% confidence level. Analyses of the primary and secondary outcomes will include all participants according to the trial arm to which they were randomized. We will use complete case analysis to handle any missing data.

To prepare the data, we will average responses to each question across the four products presented to participants to create an average score on each continuous outcome for each participant. For the identification of ultraprocessed products outcome, we will create a new binary variable indicating whether each participant correctly identified all four products as ultraprocessed or not.

We will descriptively report unadjusted means and percentages for the primary and secondary outcomes. For continuous outcomes, we will verify that Cronbach's alpha is sufficient (>0.7) and, if so, we will conduct t-tests for significance testing of our hypotheses. If Cronbach's alpha is not sufficient (>0.7), we will instead use mixed models for significance testing allowing for variation by product type. For the dichotomous outcome, we will conduct chi-squared tests for significance testing.

Exploratory Analyses

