We will examine whether participant characteristics (i.e. age, gender, educational attainment, and self-reported health status) moderate the effect of combined “ultraprocessed” and nutrient warning labels on the primary outcome, compared to nutrient warnings alone. We will also verify if understanding of the term “ultraprocessed,” measured before the experiment, moderates the effect of the combined “ultraprocessed” and nutrient warning labels, compared to nutrient warnings alone.

For these moderation analyses, we will fit a series of linear regressions (one for each potential moderator) for the continuous outcomes and logistic regressions for the binary outcome. These models will include the trial arm, the moderator, and their interaction as predictors. We will probe significant interactions by calculating the marginal effect of health warnings on the outcomes at different levels of the moderating variables.

Sample Size and Power

This study will occur in a survey that will follow a parent experiment in a virtual grocery store. The total sample size was calculated based on the primary outcomes of this parent study. To avoid contamination, this study will only include participants who were assigned to the control arm in the parent study (~1,000 participants).

Using G*Power3.1, we determined the minimum effect size we would be able to detect with this pre-determined sample size. With a two-sided alpha of 0.05 and 80% power, we would be able to detect an effect of $d=0.15$ or larger. We determined that this sample size would be enough, given that, on a smaller preliminary study that we conducted using similar labels, we found an effect size of $d=0.26$ on thinking about the risks of eating the product and of $d=0.22$ on discouragement from wanting to buy the product.

Interim Analysis

No interim analyses are planned.

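### About 1,000 participants give a minimum detectable effect of about d = 0.18, not the stated d = 0.15; power at d = 0.15 is about 66%

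*SAP*

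**What the plan says.** The sample size was inherited from a parent experiment, so the Sample Size and Power section works backwards from a fixed number to a detectable effect. It says that "this study will only include participants who were assigned to the control arm in the parent study (~1,000 participants"), and then, citing G\*Power 3.1: "With a two-sided alpha of 0.05 and 80% power, we would be able to detect an effect of $d=0.15$ or larger".

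The section then judges the number sufficient: "We determined that this sample size would be enough, given that, on a smaller preliminary study that we conducted using similar labels", effects of d = 0.26 (thinking about the risks of eating the product) and d = 0.22 (discouragement from wanting to buy it) were seen.

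The test being powered is defined earlier. Under Hypotheses, the primary comparison has two arms: participants shown the combined labels "will report a lower likelihood of purchasing the product than participants who see only nutrient warning labels (H1"). Under Main Analyses, each participant's answers are averaged over four products, and the two arms are compared by t-test if Cronbach's alpha exceeds 0.7; otherwise a mixed model is used. The same section fixes the error rate: "We will use a two-sided critical alpha of 0.05 to conduct all statistical tests".

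**The concern.** Because the sample size was not chosen for this study, the minimum detectable effect is the main content of the power section. A detectable effect of 0.15 looks too small for two groups of about 500.

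If the figure is wrong, the plan claims a sensitivity the design lacks. A reader of a null result would take the study to have had 80% power at d = 0.15, when it would miss a true effect of that size about one time in three.

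There is a secondary point. Neither preliminary effect was measured on likelihood of purchasing, the primary outcome, and the SAP gives no effect size for that outcome. Whether the sample is enough for H1 is therefore inferred from related outcomes, not shown.

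**Working it through.** **Inputs**

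- Two-sided alpha 0.05 (Main Analyses; repeated in Sample Size and Power).
- Power 80% (Sample Size and Power).
- Total N about 1,000 (Sample Size and Power).
- Two arms (Hypotheses, H1).
- One averaged score per participant, compared by two-sample t-test (Main Analyses).
- Allocation: not given in the SAP. I assume 1:1, so 500 per arm. This is the best case, because the standard error is proportional to √(1/n₁ + 1/n₂), which is smallest when the arms are equal.

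**Attempt to reproduce d = 0.15**

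Normal approximation:

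d = (z₀.₉₇₅ + z₀.₈₀) × √(2/n) = (1.960 + 0.842) × √(2/500) = 2.802 × 0.0632 = **0.177**

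The exact noncentral-t calculation gives 0.1774. The stated 0.15 is not reproduced; the recomputed value is 0.1774/0.15 = 1.18 times as large.

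**Power at d = 0.15**

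Noncentrality = 0.15 × √(500/2) = 2.372. Power ≈ Φ(2.372 − 1.960) = Φ(0.412) = 66.0%; noncentral t gives **65.9%**. The chance of missing such an effect is about 34%.

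**Sample size needed for d = 0.15**

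n = 2 × (2.802/0.15)² ≈ 698 per arm; noncentral t gives 698.6, so 699 per arm and **1,398 in total**. That is about 40% above 1,000.

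**Could another simple reading give 0.15?**

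| Variant | Minimum detectable d at 80% power |
|---|---|
| Two-sided, N = 900 | 0.187 |
| Two-sided, N = 1,000 | 0.177 |
| Two-sided, N = 1,050 | 0.173 |
| Two-sided, N = 1,100 | 0.169 |
| Two-sided, N = 1,000, 2:1 allocation | 0.188 |
| One-sided 0.05, N = 1,000 | 0.157 |
| Wilcoxon, N = 1,000 | 0.181 |
| 1,000 in each arm | 0.125 |
| Paired or one-sample, N = 1,000 | 0.089 |

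None gives 0.15. The N = 900 row also shows the effect of complete-case losses, should they leave 450 per arm (an illustration, not a SAP figure).

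**Repeated-measures reading**

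If d is expressed in single-product SD units, with four products and a common inter-product correlation r, the detectable effect is 0.1774 × √((1 + 3r)/4):

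| r | Detectable d (single-product SD) | Cronbach's alpha = 4r/(1 + 3r) |
|---|---|---|
| 0.5 | 0.140 | 0.80 |
| 0.6 | 0.148 | 0.86 |
| 0.62 | 0.150 | 0.87 |
| 0.7 | 0.156 | 0.90 |

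So 0.15 appears at r ≈ 0.62. The alpha column assumes equal item variances and equal correlations.

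**Power at other effects, N = 1,000, t-test**

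- d = 0.22: 93.5%; d = 0.26: 98.4%.
- If the purchase-likelihood effect were half the preliminary values (my assumption, d = 0.11 to 0.13): 41% to 54%.

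**The case against.** There are four arguments on the other side.

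- **Nothing operational depends on the figure.** The sample was fixed by the parent study, so correcting 0.15 changes no sample size, test or arm. The conclusion that the sample is enough survives at the preliminary effects, with 93.5% and 98.4% power. This stands, and it limits the consequence. It does not make the stated figure right.

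- **The SAP does not say which G\*Power procedure was used.** With four ratings per participant and a mixed-model fallback, a repeated-measures calculation is plausible, and it gives about 0.15 at a correlation near 0.62. This stands as a possible origin of the number but does not rescue the sentence. No correlation is stated, and the d would be in single-product SD units, whereas the t-test compares participant means. A correlation of 0.62 also implies an alpha of about 0.87, which is above 0.7, where the SAP uses the t-test. If this was the basis, the SAP has to say so.

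- **The preliminary outcomes are openly named, and discouragement from buying is close to purchase likelihood.** This is fair. Planning from a related outcome is ordinary, so this is a secondary point. The halved-effect scenario is likewise only an illustration with no source in the SAP.

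- **The planned 95% confidence intervals, not the planning figure, will show which effects the data exclude.** This is true and reduces the risk of misreading a null result, but the stated sensitivity is still incorrect.

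**Conclusion.** The concern holds. For the t-test the SAP names, with 1,000 participants split equally, the minimum detectable effect is d = 0.177 against 0.15 stated, and power at 0.15 is 65.9% against 80%. A real sample somewhat above or below 1,000 does not alter the conclusion, and unequal allocation or missing outcomes would only raise the detectable effect.

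The error lies in the stated sensitivity, not in the validity of the test or the decision to proceed. Effects from 0.15 to just under 0.18 have less than the claimed 80% power. Adequacy for H1 rests on the purchase-likelihood effect being at least about 0.18, which the cited preliminary effects make plausible but do not show directly.

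**What to change.** Replace the sentence in Sample Size and Power with wording such as: *With about 500 participants per arm, two-sided alpha 0.05 and 80% power, the minimum detectable effect is d = 0.18; power at d = 0.15 is about 66%.*

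If 0.15 came from a repeated-measures calculation, state the assumed inter-product correlation and that d is in single-product SD units, and give the t-test figure beside it.

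Add one sentence saying that the preliminary effects of 0.22 and 0.26 were not measured on likelihood of purchasing, so that adequacy for H1 assumes an effect of at least about 0.18 on that outcome.

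The cost is SAP wording only. The stated figure becomes slightly less favourable; no participants are added and no analysis changes.
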